## 11. Evaluation of safety parameters

### ff. Adverse events

Specific adverse events (AE) will be documented and investigated only during the course of

	Intervention arm (N=)	Standard of care arm (N=)
--	--------------------------	------------------------------

---

the index hospitalization (see “11.1.1.Brief summary of adverse events”). Additionally, during the first 180 days, all serious adverse events (SAEs) as defined by current Good Clinical Practice standards will be collected, fully investigated and documented in source documents and case report forms (CRF). Study duration encompasses the time from when the participant signs the informed consent until the last protocol-specific procedure has been completed (last FU at 360 days).

#### i. Brief summary of adverse events

The following AEs will be collected:

- Headaches
- Dizziness
- Fall
- Creatinine increase > 30% of baseline
- Hypokalemia < 3.5 mmol/l
- Hyperkalemia > 5 mmol/l
- Arrhythmia requiring therapy
- Systolic arterial hypotension < 80 mm Hg over 30 minutes
- Acute coronary syndrome
- Transfer to the intensive care unit
- Cardiopulmonary resuscitation

The following SAEs will be collected

- In-patient hospitalization
- Prolongation of existing hospitalization
- Life threatening event
- Death

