### **Patient Safety: Worsening Renal Function**

Some rise in creatinine and blood urea nitrogen levels is commonly seen in patients with acute HF. Often it is not possible to identify a single cause, but hypovolemia induced by diuretic treatment, low output as part of acute HF, renal venous congestion or initiation of ACE-inhibitors / ARB may play a role. Regarding the up-titration of ACE-inhibitors / ARB current guidelines suggest that changes in creatinine or blood urea nitrogen levels should not be considered clinically important unless they are rapid and substantial (41). Accordingly, a creatinine rise less than 50% from baseline values will be carefully monitored without adjustment of treatment schedule. In case of a rise of more than 50% of the baseline value, the treatment with ACE-inhibitors / ARB will be continued without augmentation and creatinine levels will be monitored every 24 hours to 48 hours. As soon as creatinine levels begin to decline, dosage of ACE-inhibitor / ARB will be up-titrated according to the treatment schedule (Figures 4a / 4b). In case of acute renal injury, defined as a doubling in serum creatinine levels compared to baseline levels (42), the following procedural schedule will be applied: A 50% reduction of the last ACE-inhibitor / ARB dosage will be performed and creatinine levels will be measured 24 hours to 48 hours later. When creatinine levels continue to rise despite this measure, a further stepwise decrease of 50% of the ACE-inhibitor / ARB is scheduled and will be repeated every 48 hours until creatinine levels begin to decline. When creatinine levels remain unchanged or decrease less than 30% of peak level, the current dosage of ACE-inhibitor / ARB will remain unchanged. As soon as creatinine levels decrease at least 30% to peak value, the initial study therapy schedule will be continued (Figures 4a / 4b). As the

dose of diuretics is an important contributor to renal injury, diuretic dose will also be reduced by at least 50% in patients with renal injury.

If systolic blood pressure still persists over 140 mm Hg despite the treatment schedule described above during day 3 to 6, higher doses of ACE-inhibitors or ARBs are recommended. The addition of a calcium-channel blocker (preferably amlodipine, Norvasc®(43) can be considered alternatively. The use of beta-blockers and spironolactone will be identical to that described in the control group.

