## **7. Study Withdrawal**

A) Discontinuation of participation of the patient due to withdrawal of consent

B) Discontinuation of participation due to:

- a) disclosure of exclusion criteria after enrolment;
- b) occurrence during participation in study of a serious new clinical event which contraindicates vasodilatation, e.g. acute stroke, acute traumatic brain injury with cerebral edema;
- c) decision of the treating medical team to switch towards palliative care

If there are findings that indicate that a further participation in the study would lead to a disproportionate risk for the patient’s health or life, the patient may be excluded from the study.

In case of an adverse event or a serious adverse event (e. g. symptomatic hypotension, acute coronary syndrome, acute kidney injury etc.) or known or unexpected side effects related to the study medication the treatment with the concerning medication will be adjusted or suspended. All other procedures remain unaffected and the patient will not be excluded from the study.

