### **10.6 Definition and Reporting of Adverse Events**

According to the Federal Law on Medicinal Products and Medical Devices (Law on Therapeutic Products - LTP) and the Federal Law on Clinical Trials with Medicinal Products (VKlin) the following predefined events that occur during trial period must be recorded and reported to the authorities:

- Adverse Events (AE)
- Serious Adverse Events (SAE)

- Suspected Unexpected Serious Adverse Reaction (SUSAR)

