### **10.6.1 Definition of Adverse Events according to the International Conference of Harmonization (ICH)**

An **Adverse Event (AE)** is any untoward medical occurrence in a patient or clinical investigation subject, who has been administered a pharmaceutical product, which does not necessarily have a causal relationship with this treatment. An adverse event can therefore be any unfavorable and unintended sign (including an abnormal laboratory finding), symptom, or disease temporally associated with the use of a medicinal (investigational) product, whether or not related to the medical (investigational) product.

A **Serious Adverse Event (SAE)** means an adverse event that requires either in-patient hospitalization, prolongation of existing hospitalization, is a congenital anomaly / birth defect, results in persistent or significant disability or incapacity, is life threatening, or results in death.

A **Suspected Unexpected Serious Adverse Reaction (SUSAR)** is defined as a serious adverse event / drug reaction, the nature or severity of which is not consistent with the applicable product information (e.g. Investigators Brochure for an unapproved investigational medicinal product).

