### **10.6.2 Reporting of Adverse Events**

AEs must be recorded by clinical investigator using the predefined section of the case report form. Annually, the sponsor reports every adverse event to Swissmedic (Swiss Agency for Therapeutic Products).

In case of SAE, the clinical investigator must inform the sponsor within 24 hours by fax or telephone using a predefined SAE reporting formulary. Furthermore the clinical investigator must report life-threatening SAE to the responsible institutional review board (IRB) or institutional ethical committee (IEC) in written form within 7 days. All other serious adverse events must be reported by the clinical investigator to the IRB / IEC within 15 days.

Life-threatening serious adverse events that fulfil the definition of a SUSAR must further be reported by the sponsor to Swissmedic using the Council for International Organization of Medical Sciences (CIOMS) formulary within seven days. The reporting deadline for all other SUSARS to Swissmedic is 15 days. Furthermore, all participating institutes have to be informed immediately by the sponsor about SUSARs. As deaths or HF rehospitalizations are part of the primary endpoint, these events will only be reported to Swissmedic in the annual AE report.

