#### ii. Display of adverse events

A supplementary material table will be produced with all adverse events if applicable and requested:

	Nr of patients with the event	Total nr of events	% of events intervention stopped	Nr of patients with the event	Total nr of events	% of events intervention stopped	p-value
Adverse events							
Headaches	xx(%)	xx	xx%	xx(%)	xx	xx%	x.xx
Dizziness	xx(%)	xx	xx%	xx(%)	xx	xx%	x.xx
Fall	xx(%)	xx	xx%	xx(%)	xx	xx%	x.xx
Creatinine increase > 30% of baseline	xx(%)	xx	xx%	xx(%)	xx	xx%	x.xx
Hypokalemia < 3.5 mmol/l	xx(%)	xx	xx%	xx(%)	xx	xx%	x.xx
Hyperkalemia > 5 mmol/l	xx(%)	xx	xx%	xx(%)	xx	xx%	x.xx
Arrhythmia requiring therapy	xx(%)	xx	xx%	xx(%)	xx	xx%	x.xx
Systolic arterial hypotension*	xx(%)	xx	xx%	xx(%)	xx	xx%	x.xx
Acute coronary syndrome	xx(%)	xx	xx%	xx(%)	xx	xx%	x.xx
Transfer to the intensive care unit	xx(%)	xx	xx%	xx(%)	xx	xx%	x.xx
Cardiopulmonary resuscitation	xx(%)	xx	xx%	xx(%)	xx	xx%	x.xx
Serious adverse events							
Death	xx(%)	xx	xx%	xx(%)	xx	xx%	x.xx
In-patient hospitalization	xx(%)	xx	xx%	xx(%)	xx	xx%	x.xx
Prolongation of existing hospitalization	xx(%)	xx	xx%	xx(%)	xx	xx%	x.xx
SAE other than any of the above	xx(%)	xx	xx%	xx(%)	xx	xx%	x.xx

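### The SAP narrows the protocol's adverse-event scope and time window, and plans no by-arm comparison of the protocol's own definition of acute renal injury

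*Combined protocol and SAP*

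**What the plan says.** **Protocol.** Section 10.6.1 says that an AE "is any untoward medical occurrence in a patient or clinical investigation subject", and counts abnormal laboratory findings. Section 10.6 sets the window: "the following predefined events that occur during trial period must be recorded and reported to the authorities". Under 10.6.2, "AEs must be recorded by clinical investigator using the predefined section of the case report form", and "Annually, the sponsor reports every adverse event to Swissmedic".

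On the kidney, section 5 (Patient Safety: Worsening Renal Function) has three levels. Below a 50% rise, creatinine is watched and the schedule is unchanged. Above 50%, up-titration is held. The third level reads "In case of acute renal injury, defined as a doubling in serum creatinine levels compared to baseline levels". Section 7 gives as examples of adverse or serious adverse events "symptomatic hypotension, acute coronary syndrome, acute kidney injury etc".

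**SAP.** Section 11.1 documents specific AEs during the index hospitalization only, and all SAEs for the first 180 days. Section 11.1.1 lists eleven AEs; the single renal item is "Creatinine increase > 30% of baseline". It also lists four kinds of SAE. Section 11.1.2 lays out the by-arm table, introduced as follows: "A supplementary material table will be produced with all adverse events if applicable and requested". Its SAE rows are death, in-patient hospitalization, prolonged hospitalization and a residual row for any other SAE. Section 11.1.3 compares AE rates by arm with a chi-square test. Section 11.4 states that no further safety analysis is planned. The assessment schedule (SAP 3.5) has an active search for AEs and SAEs in hospital and again at days 90, 180 and 360.

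**The concern.** Safety is part of the primary objective (SAP 2.1). Protocol section 6 names arterial hypotension, with a resulting fall in blood flow to the kidney and other major organs, as the main potential harm of the intervention. One would therefore expect the analysis plan to isolate the renal harm that the protocol itself defines. It does not: the one renal row starts at a level on which the protocol takes no action and has no upper tier.

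The scope and window also differ between and within the documents. An unlisted non-serious AE is recordable under the protocol but has no place in the SAP. An AE after discharge is inside the protocol's window and the SAP's visit schedule, but outside the window in SAP 11.1.

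At stake is whether the trial can report, from a prespecified analysis, how often protocol-defined renal injury and other named serious events occurred in each arm. A threshold chosen after the data are seen would be weaker evidence.

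**Working it through.** There is no stated figure to reproduce. The check compares the texts and then does threshold arithmetic.

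**1. Texts side by side**

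| Item | Protocol | SAP |
|---|---|---|
| AE scope | Any untoward occurrence (10.6.1) | Eleven listed events (11.1.1), plus all SAEs |
| AE window | Trial period (10.6) | Index stay; SAEs to 180 days (11.1). Schedule searches to day 360 (3.5) |
| Renal levels | Rise above 50%; doubling = acute renal injury | Rise above 30% only |
| Stroke | Named as a serious new event (section 7) | Inside a seriousness row, not identifiable |
| Life-threatening event | Part of the SAE definition (10.6.1) | Collected (11.1.1), no row of its own (11.1.2) |

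**2. Nesting.** As ratios to baseline the levels are 1.30, 1.50 and 2.00. Since 2.00 > 1.30, every sampled doubling is in the SAP row. Cases are merged with milder rises, not lost.

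**3. How mixed is the row?** The documents give no creatinine distribution, so this is assumed: the log of the ratio to baseline is normal with mean 0, and a share p exceeds 1.30. Then SD = ln(1.30) / z(p).

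- p = 20%: SD = 0.2624 / 0.8416 = 0.312. P(>1.50) = 1 − Φ(0.4055/0.312) = 9.7%. P(>2.00) = 1 − Φ(0.6931/0.312) = 1.3%. Share of the row below 50%: 1 − 9.7/20 = 52%. Share below doubling: 1 − 1.3/20 = 93%.
- p = 30%: SD = 0.2624 / 0.5244 = 0.500. P(>1.50) = 20.9% and P(>2.00) = 8.3%. Shares: 1 − 20.9/30 = 30% and 1 − 8.3/30 = 72%.

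**4. Could the row hide an excess of doublings?** Take the planned 385 per arm and the 20% case, so the control arm has 77 patients above 30% and about 5 doublings (385 × 1.3%). Suppose the intervention arm has 15 doublings: 5 vs 15 gives Fisher p = 0.039. What the >30% row shows depends on how the excess arises.

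- *Mean shift.* 15/385 = 3.9%, z = 1.763, so mean = 0.6931 − 1.763 × 0.312 = 0.144. P(>1.30) = 35.2%, or 135 vs 77, p about 4 × 10⁻⁶. The row shows the harm more clearly than doubling does.
- *Wider spread only.* SD = 0.6931 / 1.763 = 0.393. P(>1.30) = 25.2%, or 97 vs 77, p = 0.10. The row is less clear than doubling.
- *Assumed worst case.* All the extra doublings occur in patients who would have passed 30% anyway: 77 vs 77, p = 1.0. This is a constructed extreme and does not follow from the log-normal model.

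Masking is therefore possible but not to be expected in general.

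**The case against.** A reader might infer two stronger things. The documents support neither.

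*That renal injury cannot be compared by arm.* Protocol section 5 measures creatinine in both groups at inclusion, every 24 to 72 hours in the first week, and at discharge, so doubling can be derived. Creatinine at 48 hours and at discharge is also a secondary endpoint with a between-arm row in SAP Table 3. That row does not fill the gap, however. It is shown as mean and SD, and SAP 10.2.3 prescribes a Mann–Whitney test, which is insensitive to a small excess in the upper tail. The intervention arm's ACE-inhibitor/ARB up-titration schedule runs to day 7, so the 48-hour value precedes most of it, and a discharge value can miss a peak that has resolved.

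*That only eleven kinds of event are collected.* All SAEs are collected for 180 days, and the residual row gives any unlisted SAE a by-arm count and p-value. Only unlisted non-serious AEs have no place.

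Three further defences carry weight. The protocol's 50% and 100% levels guide treatment and are not labelled as analysis endpoints, and a reporting threshold may properly be more sensitive than a treatment threshold. But section 7 does name acute kidney injury among adverse events, so a row for it is a fair expectation. Second, the conditional wording governs the display, while the comparison in SAP 11.1.3 is unconditional. But that section names no event categories, so without the table readers may not see the comparison event by event. Third, the protocol refers to predefined events and a predefined case report form section, and SAP 5.6 to predefined AEs, which leaves room for a closed list. But the protocol prints no such list and also says that every AE is reported.

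**Conclusion.** The point holds as a gap in the planned analysis and a mismatch between texts, not as a loss of data. Three things stand.

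1. AE scope and window differ between protocol 10.6 and SAP 11.1, and between SAP 11.1 and the SAP's own schedule.
2. No planned analysis compares protocol-defined acute renal injury by arm. It is pooled in a row of which roughly 72% to 93% might be milder than that definition. This range rests wholly on the assumed log-normal changes and an assumed 20% to 30% of patients above a 30% rise.
3. SAEs are sorted by seriousness, so a stroke is counted but not identifiable; life-threatening events have no row of their own; and the table is conditional.

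The >30% row would often pick up a renal signal, and under a general upward shift in creatinine would do so strongly. The case for extra tiers is that this is not assured and that the severity of any signal would stay unknown. The primary efficacy analysis is unaffected. This should be changed because it is cheap and serves the stated safety objective.

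**What to change.** In SAP 11.1.1 and 11.1.2:

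- Keep the >30% creatinine row and add by-arm rows for a rise above 50% and a rise of at least 100%, derived from the serial values already collected. Note that sampling every 24 to 72 hours can miss short peaks.
- Show SAEs by event term, so that stroke can be seen, as well as by seriousness, with a row for life-threatening events.
- Delete the condition on producing the table.
- Reconcile AE scope and time window across protocol 10.6 to 10.6.2, SAP 11.1 and the schedule in SAP 3.5. State whether non-serious AEs outside the list are recorded, and whether the searches at days 90, 180 and 360 cover AEs or only SAEs.

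These are reporting categories and change no treatment rule. The cost is some coding of event terms and a longer supplementary table, with no new patient procedures. If the scope is reconciled towards the protocol's wider wording, any AEs recorded outside the list also need to be coded and tabulated.

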#### ii. Display of adverse events

A supplementary material table will be produced with all adverse events if applicable and requested:

	Nr of patients with the event	Total nr of events	% of events intervention stopped	Nr of patients with the event	Total nr of events	% of events intervention stopped	p-value
Adverse events							
Headaches	xx(%)	xx	xx%	xx(%)	xx	xx%	x.xx
Dizziness	xx(%)	xx	xx%	xx(%)	xx	xx%	x.xx
Fall	xx(%)	xx	xx%	xx(%)	xx	xx%	x.xx
Creatinine increase > 30% of baseline	xx(%)	xx	xx%	xx(%)	xx	xx%	x.xx
Hypokalemia < 3.5 mmol/l	xx(%)	xx	xx%	xx(%)	xx	xx%	x.xx
Hyperkalemia > 5 mmol/l	xx(%)	xx	xx%	xx(%)	xx	xx%	x.xx
Arrhythmia requiring therapy	xx(%)	xx	xx%	xx(%)	xx	xx%	x.xx
Systolic arterial hypotension*	xx(%)	xx	xx%	xx(%)	xx	xx%	x.xx
Acute coronary syndrome	xx(%)	xx	xx%	xx(%)	xx	xx%	x.xx
Transfer to the intensive care unit	xx(%)	xx	xx%	xx(%)	xx	xx%	x.xx
Cardiopulmonary resuscitation	xx(%)	xx	xx%	xx(%)	xx	xx%	x.xx
Serious adverse events							
Death	xx(%)	xx	xx%	xx(%)	xx	xx%	x.xx
In-patient hospitalization	xx(%)	xx	xx%	xx(%)	xx	xx%	x.xx
Prolongation of existing hospitalization	xx(%)	xx	xx%	xx(%)	xx	xx%	x.xx
SAE other than any of the above	xx(%)	xx	xx%	xx(%)	xx	xx%	x.xx

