Recent evidence from pilot studies for a long-term benefit of early aggressive therapeutic intervention in acute HF and the promising results obtained by vasodilatation with nitrates and hydralazine in chronic HF provide the rationale for our hypothesis that an early goal-directed decrement of preload and afterload with a target systolic blood pressure of 90 mm Hg to 110 mm Hg by aggressive vasodilatation in patients with acute HF in the non-ICU setting is safe, and leads to a better clinical and economical outcome. The early goal directed therapy as implemented by our protocol is expected to result in a more rapid resolution of symptoms, reduced time to discharge and reduced disease severity at the time of discharge. In addition, patients in the intervention group will receive a significantly higher dose of disease-modifying drugs like ACE-inhibitors and ARBs at the time of discharge. The difference in the dose of ACE-inhibitors and ARBs between both groups is expected to prevail within the first months of follow-up. The combination of both, improved disease state at discharge and higher doses of disease-modifying drugs during most of the study period is expected to result in a significant improvement in patient morbidity and mortality (11,28). This project is well in line with our previous research in this setting (10,29–31).

**Figure 3:** Theoretical model of expected effects of two different treatment strategies on quantitative markers of HF (B-type natriuretic peptide (BNP) or pulmonary capillary wedge pressure (PCWP)). Due to the aggressive preload and afterload decrement especially during the first 48 h of early goal directed treatment therapy, B-type natriuretic peptide and pulmonary capillary wedge pressure are expected to decrease faster and more pronounced than in the standard of care group.

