64 **iv. Endpoint tables**

65 The following table will be produced and

66 Table 3 will be provided in the main publication:

67

68 **Table 3: Primary and secondary endpoint events**

Event	Intervention arm (N=)	Standard of care arm (N=)	Hazard Ratio (95%CI)	p-value
Primary composite endpoint – no. (%)†	xx (xx%)	xx (xx%)	x.xx (x.xx-x.xx)	x.xx
All-cause mortality — no. (%)	xx (xx%)	xx (xx%)	x.xx (x.xx-x.xx)	x.xx
Heart failure hospitalization – no. (%)	xx (xx%)	xx (xx%)	x.xx (x.xx-x.xx)	x.xx
Secondary endpoints – no. (%)	xx (xx%)	xx (xx%)	x.xx (x.xx-x.xx)	x.xx
All-cause mortality at 180 days.— no. (%)	xx (xx%)	xx (xx%)	x.xx (x.xx-x.xx)	x.xx
Heart failure hospitalization – no. (%)	xx (xx%)	xx (xx%)	x.xx (x.xx-x.xx)	x.xx
Death or re-hospitalization at 180 days. — no. (%)	xx (xx%)	xx (xx%)	x.xx (x.xx-x.xx)	x.xx
Need for ICU admission during initial hospitalization — no. (%)	xx (xx%)	xx (xx%)	x.xx (x.xx-x.xx)	x.xx
Acute coronary syndrome during initial hospitalization — no. (%)	xx (xx%)	xx (xx%)	x.xx (x.xx-x.xx)	x.xx
Symptomatic hypotension during initial hospitalization — no. (%)	xx (xx%)	xx (xx%)	x.xx (x.xx-x.xx)	x.xx
B-type natriuretic peptide (BNP) level – ng/l (±SD)	xx±xx	xx±xx	x.xx (x.xx-x.xx)	x.xx
at 48 hours	xx±xx	xx±xx	x.xx (x.xx-x.xx)	

69

	Intervention arm				Standard of care arm				Intervention vs standard of care	
	Baseline (N=)	Follow-up (N=)	Change FU vs Baseline	p-value	Baseline (N=)	Follow-up (N=)	Change FU vs Baseline	p-value	Mean difference of the change	p-value
at discharge										
Creatinine level – µmol/l (±SD)		XX±XX			XX±XX				x.xx (x.xx-x.xx)	
at 48 hours										
at discharge		XX±XX			XX±XX				x.xx (x.xx-x.xx)	
Changes in circumferences of both legs during initial hospitalization – cm (±SD)		XX±XX			XX±XX				x.xx (x.xx-x.xx)	
Blood pressure course over the first 6 days – mmHg (±SD)		XX±XX			XX±XX				x.xx (x.xx-x.xx)	
Time to disappearance of a third heart sound (if present initially) – days (±SD)		XX±XX			XX±XX				x.xx (x.xx-x.xx)	
Quality of life assessed at 90 days (±SD)	N= xx	N= xx	N= xx	x.xx	N= xx	N= xx	N= xx	x.xx	N= xxx	
Total triAS scale – mean score (±SD)	xx±xx	xx±xx	xx±xx	x.xx	xx±xx	xx±xx	xx±xx	x.xx	xx±xx	x.xx
Fractures due to fall within 180 days and 360 days – no. (%)		xx (xx%)			xx (xx%)				x.xx (x.xx-x.xx)	
Death or HF re-hospitalization at 360 days – no. (%)		xx (xx%)			xx (xx%)				x.xx (x.xx-x.xx)	

70

71

72

73

74

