### **iv. Listing of adverse events by patient**

Listing of adverse events per patient are provided on request.

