#### **ii. Other safety evaluations**

##### **11.1.1. Other observations related to safety**

No other safety observations, assessments or analyses are currently defined and planned for this statistical analysis plan.

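### Supplemental Table 1 sorts SAEs by seriousness, not cause: HF and non-HF admissions appear to share one row, and stroke has no outcome row

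*Combined protocol and SAP*

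**What the plan says.** The aim in SAP 2 (Primary objective) is to determine both safety and efficacy. The safety output is set out in SAP 11:

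- **SAE rows.** The SAE block of Supplemental Table 1 (SAP 11.1.2) has four rows: death, in-patient hospitalization, prolongation of hospitalization, and "SAE other than any of the above". SAP 11.1.1 also lists "Life threatening event" among the SAEs to collect, but the table has no such row.
- **Test.** The table has a p-value column, and SAP 11.1.3 plans a two-sided chi-square comparison of arms on the ITT set. For the safety population it counts events only up to the last confirmed intake of study drug, meaning hydralazine or nitrates.
- **Windows.** SAP 11.1: "Specific adverse events (AE) will be documented and investigated only during the course of" the index hospitalization. SAEs of all kinds are to be collected, fully investigated and documented for 180 days.
- **Status.** The table is to be produced if applicable and requested. SAP 11.1.4: "Listing of adverse events per patient are provided on request". SAP 11.4: "No other safety observations, assessments or analyses are currently defined and planned for this statistical analysis plan".
- **Exposure after discharge.** Protocol 1: "The difference in the dose of ACE-inhibitors and ARBs between both groups is expected to prevail within the first months of follow-up".
- **Stroke.** Protocol 7 lists, among reasons for discontinuation, "a serious new clinical event which contraindicates vasodilatation, e.g. acute stroke".

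**The concern.** The intervention differs from control in two ways with different time courses. Nitrates and hydralazine end in hospital. The ACE-inhibitor/ARB dose difference is meant to continue for months. Renal, hypotensive or cerebrovascular harm could therefore arise after discharge. By then the diagnosis-type AE rows have probably ended and the safety-population window has closed. Scheduled creatinine and electrolyte measurement also stops at discharge (Protocol 5, General Procedure for Both Groups), which leaves SAE reports as the main planned route by which later renal harm would be recorded.

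The planned table would show those SAEs by seriousness criterion. If HF readmissions sit in the hospitalization row, that row mixes the event the treatment is meant to prevent with the events it might cause. A similar total in both arms could be read as no harm.

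**Working it through.** **1. Row and window inventory (no arithmetic).**

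| Display | Rows that name a cause | Window |
|---|---|---|
| Supplemental Table 1, SAE block | none of four | 180 days |
| Supplemental Table 1, AE block | fall, creatinine rise, potassium, arrhythmia, hypotension, acute coronary syndrome and others | index stay (SAP 11.1); some doubt from SAP 3.5 |
| Table 3, in-hospital rows | acute coronary syndrome, symptomatic hypotension, creatinine | index stay |
| Table 3, later rows | HF hospitalization; fractures due to falls | 180 or 360 days |

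The other later rows of Table 3, including "Death or re-hospitalization at 180 days", give no cause. Stroke appears as baseline history (Table 1), as an example in a date check (SAP 4.2) and as a discontinuation reason (Protocol 7). It is never an outcome.

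**2. Do HF readmissions enter the hospitalization row?** Probably. Protocol 10.6.1 defines any event requiring in-patient hospitalization as serious. Protocol 10.6.2 exempts deaths and HF rehospitalizations from separate reporting to the regulator but keeps them in the annual adverse event report. SAP 11.1 collects all SAEs. The footnote to the rehospitalization line in SAP 3.5, which asks whether it is an SAE, leaves some doubt.

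**3. Illustration of offset.** Assumptions, not document figures: 385 per arm (the planned size), one admission per patient, control vs intervention HF admissions 96 vs 77 and non-HF admissions 39 vs 58.

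- Combined row: 96 + 39 = 135; 77 + 58 = 135.
- With overlap (independence) instead of addition: 1 − 0.75 × 0.90 = 32.5% vs 1 − 0.80 × 0.85 = 32.0%. The offset remains.
- Recovery by subtracting HF events: 39 vs 58 if reported and adjudicated HF counts agree. If 10% of reported HF admissions are not confirmed: 39 + 9.6 = 48.6 vs 58 + 7.7 = 65.7.
- Table 3 composites with 12% deaths in each arm: death or HF 1 − 0.88 × 0.75 = 34.0% vs 1 − 0.88 × 0.80 = 29.6%; death or any readmission 1 − 0.88 × 0.675 = 40.6% vs 1 − 0.88 × 0.68 = 40.2%. The gap closes, which points to a non-HF excess but not to its cause.

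**4. What a cause row adds.** Newcombe 95% interval for the difference d = p2 − p1, with Wilson limits (l, u) per arm: lower d − √[(p2 − l2)² + (u1 − p1)²], upper d + √[(u2 − p2)² + (p1 − l1)²].

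Stroke 4 vs 12: p1 = 1.04% (0.41 to 2.64), p2 = 3.12% (1.79 to 5.37), giving +2.1 points (0.0 to 4.4). The same formula gives the other rows. All other non-HF causes are set equal between arms, at 35 each for stroke and 31 each for kidney injury.

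| Assumed events | Own row, points (95% CI) | Non-HF total, perfectly subtracted |
|---|---|---|
| Stroke 4 vs 8 | +1.0 (−0.9 to 3.1) | 39 vs 43: +1.0 (−3.4 to 5.5) |
| Stroke 4 vs 12 | +2.1 (0.0 to 4.4) | 39 vs 47: +2.1 (−2.4 to 6.6) |
| Acute kidney injury 8 vs 20 | +3.1 (0.4 to 6.0) | 39 vs 51: +3.1 (−1.5 to 7.7) |

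Fisher p for the own rows: 0.38, 0.074 and 0.032.

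**5. Power, because the plan does test.** Two-proportion normal approximation, pooled variance under the null, two-sided 5%, non-HF admission 10% vs 15%:

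- Separate non-HF row: 55%.
- Combined row, with control HF admission 15–35% and HF risk ratio 0.8–1.0: 5% to 27%.
- All-cause composite, adding equal deaths of 8–20%: 5% to 21%.

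**The case against.** Several points on the other side stand.

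- **The gap is in summarising, not collection.** A reader might infer that harm after discharge goes unrecorded. It does not: SAEs are to be fully documented to 180 days, and the schedule in SAP 3.5 searches for AEs and SAEs at days 90, 180 and 360.
- **The index-stay limit is not certain.** That same schedule is in tension with SAP 11.1. If the AE rows ran through follow-up, acute coronary syndrome, creatinine rise, hypotension and falls would have rows after discharge. Stroke still would not.
- **Table shells are not exhaustive.** Table 3 as extracted lacks rows for several listed endpoints, such as time to discharge and cost, so a missing row is weak evidence that nothing is planned. For stroke the inference is stronger: it is not a listed endpoint, and SAP 11.4 plans no other safety analysis.
- **Stroke is not named as an expected harm.** It is tempting to read Protocol 7 that way, but it gives stroke, beside traumatic brain injury, as a reason to stop vasodilatation. Protocol 6 names hypotension with reduced renal and other organ blood flow as the main potential harm, and hypotension and creatinine rise both have AE rows.
- **The excess would not be wholly hidden.** Subtraction with Table 3 roughly recovers the non-HF total. What it cannot give is the cause.
- **The numbers are chosen.** The 135 vs 135 example was picked to cancel exactly. At 4 vs 8 strokes, a separate row does not settle the question either.

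**Conclusion.** The point holds as a cheap improvement to reporting. None of the four SAE rows names a cause, the one hospitalization row probably mixes HF and non-HF admissions, and stroke has no outcome row on any reading. That HF hospitalization and fall fractures are the only causes summarised after discharge depends on taking SAP 11.1 at its word over the schedule. The safety-population analysis does not fill the gap, because it ends with the last nitrate or hydralazine dose.

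The effect cannot be sized from the documents. Under the assumptions shown, the interval for a 4 vs 12 stroke difference is about half as wide in its own row as in the non-HF total (4.4 against 9.0 points), and for kidney injury about 60% as wide (5.6 against 9.2 points). These are illustrations, not predictions.

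A reader might go further and conclude that the trial cannot assess safety or that its main result is compromised. The documents do not support that: the underlying records are to exist, several in-hospital harms are tabulated and tested, and the primary analysis is unaffected.

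**What to change.** Amend SAP 11.1.2 as follows.

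1. Produce the table always, on the ITT set already named in SAP 11.1.3, with SAEs to 180 days.
2. Split hospitalization into three rows: HF confirmed by adjudication, reported as HF but not confirmed, and non-HF. The middle row keeps unconfirmed HF admissions out of the harm count.
3. Add rows for serious stroke, acute kidney injury, syncope or injurious fall, and acute coronary syndrome. Show patients with at least one event, the difference between arms and its 95% CI. Give each a brief definition.
4. Add the life-threatening row that SAP 11.1.1 already collects, and keep the existing seriousness rows.
5. Code causes blind to arm. The trial is open label, and SAP 2.3 promises blinded adjudication only for the primary endpoint. Naming the rows now also avoids choosing them after results are seen.

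No new data collection is planned, since SAP 11.1 already requires SAEs to be documented. The cost is coding work, a longer table, and possibly source checks for records captured before the April 2016 move to a single database (SAP 4.1).
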